Patients lost to follow-up before experiencing EDA will be considered as not having had the event. A sensitivity analysis with the maximum bias assumption will be conducted by considering missing data (discontinuation of follow-up before the end of the 2-year follow-up with NEDA) in the interventional arm as failures (non-responders = EDA) and those in the control arm as successes (responders = NEDA).

The rate of EDA in both arms will be estimated and then compared between the two treatment arms using mixed-effects logistic regression (random center effect). The treatment arm will be the factor of interest in the model. Adjustment will be made for randomization stratification factors (center, contrast enhancement on diagnostic brain and spinal cord MRI), known prognostic factors listed in section 4.1.4 of the protocol (Age, Gender, Presence of contrast enhancement on the reference MRI, Lesion load in FLAIR in mm³, Number of lesions with contrast enhancement on the reference MRI, EDSS score at baseline), and the time between CIS and the first administration of the treatment, which varies among patients (from a few days to 95 days = maximum of 90 days between CIS and the reference MRI and the first administration of the study treatment, which takes place on the first Saturday post-MRI). Adjustment for the center effect will be performed by considering the center as a random effect in the model (Kahan 2014, Kahan et al. 2015, Edgar et al. 2021).

The number of lesions with contrast enhancement on the reference MRI could not be determined quantitatively. This information is provided by recording the presence of contrast enhancement with a precision level in 3 modalities (similar to the diagnostic MRI): no lesions with contrast enhancement, one lesion with contrast enhancement, and at least two lesions with contrast enhancement. This information will be used as an adjusting variable only if it is not significantly associated with contrast enhancement on the diagnostic MRI (a randomization stratification factor), for which an adjustment is performed. The statistical significance of the association will be assessed using the Chi-square test or Fisher's exact test if the Chi-square test is not applicable, with a significance level set at < 0.05.

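### A listed prognostic covariate enters both primary models only if it is not significantly associated with the stratification factor, a test that does not measure redundancy and leaves the covariate set open

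*SAP*

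**What the plan says.** In the SAP section Primary Analysis (Rate of EDA), the mixed logistic model is to be adjusted for the stratification factors and for "known prognostic factors listed in section 4.1.4 of the protocol". The list given there has two entries for enhancement on the same scan: "Presence of contrast enhancement on the reference MRI" and, later, "Number of lesions with contrast enhancement on the reference MRI, EDSS score at baseline".

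The next paragraph explains that the count could not be obtained as a number and was recorded in three levels: "no lesions with contrast enhancement, one lesion with contrast enhancement, and at least two lesions with contrast enhancement". It then sets the entry rule: "This information will be used as an adjusting variable only if it is not significantly associated with contrast enhancement on the diagnostic MRI". Chi-square is the default test, Fisher's exact the fallback, and the threshold is 0.05. The only reason given is that the diagnostic-MRI factor is already one "a randomization stratification factor), for which an adjustment is performed".

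The section Primary Analysis (Time to EDA) gives the Cox model the same adjustment variables as the logistic model, so one pre-test settles the covariates of both primary analyses.

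**The concern.** The count is in the list because it is thought to predict disease activity. The entry rule does not ask about that. It asks whether the count is detectably related to another covariate already in the model. Two related baseline covariates can both be worth adjusting for. A p-value reflects the strength of the association and the number of patients together, so at a fixed significance level it says whether an association can be detected, not whether the second variable adds nothing to the first.

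Two things are at stake. The first is some precision, if a prognostic variable is left out. The second is the definition of the primary effect. Odds and hazard ratios are non-collapsible, so the conditional ratio depends on the covariates in the model, and here that set is not known until the pre-test is run. In addition, the two listed reference-MRI variables overlap, and the text does not say how they are to be handled together.

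**Working it through.** **Inputs.** The SAP states no figure for this rule, so there is none to reproduce.
- Number of patients: 316, the denominator the SAP uses for FLAIR lesion load; 258 (those with retrievable images) serves as a low-end case.
- Table: diagnostic enhancement with/without by reference-MRI count in three levels, so 2 x 3 with 2 degrees of freedom. The SAP also says the diagnostic MRI was graded in a similar three-level form, so 3 x 3 (4 degrees of freedom) is a sensitivity case.
- Significance level: 0.05.
- True strength of association: not given, so a range is shown.

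**When the covariate is dropped.** The chi-square statistic equals N·V² in a 2 x 3 table. The critical value at 2 degrees of freedom is 5.99. The smallest observed V that excludes the covariate is therefore √(5.99/316) = 0.138 (√(5.99/258) = 0.152 at the lower number). Approximate variance inflation is 1/(1 − V²), which is 1/(1 − 0.138²) ≈ 1.02 at that point. Even at V = 0.5 it is 1/(1 − 0.25) ≈ 1.33. The rule acts long before collinearity would matter.

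**How often it is dropped.** P(drop) = 1 − F(critical value; df, λ), where F is the non-central chi-square distribution function and λ = N·w². In a 2 x 3 table the effect size w equals V.

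| w | λ at N = 316 | 2 x 3, N = 316 | 2 x 3, N = 258 | 3 x 3, N = 316 |
|---|---|---|---|---|
| 0.10 | 3.16 | 34% | 28% | 26% |
| 0.15 | 7.11 | 66% | 57% | 55% |
| 0.20 | 12.64 | 90% | 83% | 83% |
| 0.25 | 19.75 | 98% | 96% | 96% |

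At w = 0.05 the 2 x 3 figure with 316 patients is 11%. It passes 50% at V = 0.125. As odds ratios, assuming enhancement in 30–50% on the diagnostic MRI and in 15–25% on the reference MRI among those without diagnostic enhancement, P(drop) is 19–29% at an odds ratio of 1.5, 54–72% at 2 and 95–99% at 3.

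**What the SAP itself presumes.** Under its missing-data rules, an unknown diagnostic enhancement status is filled in from the baseline MRI. One scan is treated there as a stand-in for the other, yet the entry rule keeps the covariate only if no association is detected.

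**Consequence for the treatment comparison.** Simulation with 316 patients, 2000 runs per scenario and no centre effect. The assumed odds ratios were 2 or 4 between the scans, 1.5 or 2.5 for prognosis, and 0.5 for treatment.
- Rejection with no treatment effect: 4.9–5.6% under the rule, 5.0–5.2% with forced inclusion. The Monte Carlo standard error is √(0.05 × 0.95/2000) ≈ 0.5 points.
- Power, forced inclusion against the rule: 83.9 v 83.5%, 82.6 v 80.4%, 84.2 v 83.5% and 82.1 v 78.8%. The losses are 0.4, 2.2, 0.7 and 3.3 points.
- Median treatment odds ratio: 0.505–0.536 without the covariate, 0.492–0.500 with it.

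A second simulation (1500 runs; log odds ratios 0, 0.6 and 1.0 over the three levels, −0.6 for treatment) gave power of 72.1% with the three-level variable, 71.4% with presence only and 70.1% with neither.

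**Presence and count side by side.** Presence is the three-level variable collapsed: yes = one or at least two. If both are entered, one column is the sum of two others. If the count is dropped, the text does not say whether presence goes too.

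**The case against.** The strongest reply is that the rule is harmless. It is fixed before data lock and uses neither outcome nor arm, so it cannot favour a treatment. A reader might infer bias or an inflated type I error from the term pre-test; neither the text nor the simulation supports that. If presence stays in the model, only the distinction between one and at least two lesions is lost. The second simulation puts that at 72.1 − 71.4 = 0.7 points, when each power figure has a Monte Carlo standard error of √(0.72 × 0.28/1500) ≈ 1.2 points. All of this stands.

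Three other stronger readings also go further than the document allows.
- That the covariate will usually be discarded: this needs a V of about 0.125 or more. The imputation rule makes an association plausible but does not give its strength.
- That there is no reason for the rule: the SAP does give one, namely that a related factor is already adjusted for. It is a weak reason, because the test does not measure redundancy, but it is stated.
- That the model will be rank-deficient: the text can also be read as describing one three-level variable that carries both presence and number. It is ambiguous rather than demonstrably wrong, and even if both were entered, the treatment coefficient would remain estimable.

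Finally, unconditional entry is not quite free. The SAP has no missing-value rule for reference-MRI enhancement as a covariate, although its rule for the diagnostic status anticipates that the baseline status may be missing.

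**Conclusion.** The point holds as a matter of specification and modest efficiency, not of validity. A listed prognostic factor is kept or dropped by a criterion that excludes it from an observed V of about 0.14, with variance inflation of about 1.02. The drop probabilities rest on 316 patients, a 2 x 3 table and the assumed range of V. The power cost of roughly 0.4 to 3 points rests on assumed prognostic and treatment effects that the SAP does not give, and is at the low end if presence is retained. What does not depend on those assumptions is that the covariate set of both primary models, and so the conditional odds or hazard ratio, is not fixed in advance, and that two analysts could code the reference-MRI information differently from the same text.

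**What to change.** Delete the pre-test. State that one reference-MRI enhancement variable with three levels (none, one, at least two) enters the logistic and Cox models unconditionally, in place of the separate presence variable and alongside the diagnostic-MRI stratum. Add a missing-value rule so that no patient drops out of the primary models, for example a missing category like the one the SAP already uses for the T2/FLAIR lesion count.

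This is a change of SAP wording and needs no new data. It costs one extra degree of freedom compared with a model holding presence only, or two compared with a model holding neither, plus one if the missing category is used.

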Statistical Analysis Plan

December 21st, 2023

NCT01817166

PHRC-N/2012/ET-01

Efficacy of Cholecalciferol (Vitamin D3) for Delaying the Diagnosis of MS After a Clinically Isolated Syndrome

Final detailed statistical analysis plan drafted before data lock and before the commencement of statistical analyses.

An initial data analysis will provide a description of each arm. Statistical results will be presented using mean and standard deviation for quantitative variables with a Gaussian distribution, and median and interquartile range for other quantitative variables. For qualitative variables, frequencies and associated percentages will be presented.

Demographic, clinical (initial relapse), radiological (diagnostic MRI), and biological (lumbar puncture, vitamin D) data will be described. In particular, it will be determined for each patient whether the diagnostic criteria of McDonald 2017 are met at inclusion (Thompson et al., 2018).

The statistical analysis will be conducted by the BESPIM of the CHU de Nîmes using R 4.1.1 or a later version (R Core Team (2021). R Foundation for Statistical Computing, Vienna, Austria).

Primary Analysis (Rate of EDA)

The primary objective is to assess the efficacy and tolerance over 2 years of treatment with Cholecalciferol (Vitamin D3) in patients who have experienced a clinically isolated syndrome at high risk of multiple sclerosis (CIS, according to the McDonald criteria of 2005). This efficacy will be measured by comparing the risk of conversion to relapsing-remitting multiple sclerosis (RRMS) within 2 years after CIS, according to 2005 McDonald criteria (new lesions on follow-up brain and spinal cord MRIs or new relapses) (McDonald et al., 2001; Polman et al., 2005), between the arm receiving Cholecalciferol and the arm receiving the placebo.

Following the actual diagnostic criteria for MS (McDonald 2017), most patients present with a diagnosis of active MS and conversion corresponds to the current concept of EDA (evidence of disease activity defined by clinical relapses or imaging (gadolinium-enhancing lesions or new or unequivocally enlarging T2/FLAIR lesions) (Lublin et al., 2013) an "no conversion" corresponds to NEDA (no evidence of disease activity). Hence, the event will be the occurrence of EDA within the two years of follow-up (relapse and/or appearance of new or enlarging lesions (NEL) on follow-up MRIs at 3, 12, and 24 months).

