Furthermore, the lesion load in FLAIR in mm³ (reference MRI) is available only for 258 out of 316 patients (those for whom the MRI images could be retrieved). Moreover, obtaining this volume is not reliable because the software does not provide a sufficiently precise estimate. Therefore, no adjustment will be made for the lesion load, and the number of T2/FLAIR lesions on the reference MRI will be used instead as an indicator of lesion load (in 2 modalities: <9 lesions, >= 9 lesions).

In the event of the use of an incorrect stratum during randomization (randomization performed for the stratum with contrast enhancement on the diagnostic MRI while the true value was an absence of contrast enhancement, and vice versa), the analyses will be adjusted for the contrast enhancement value on the diagnostic MRI (Yelland et al., 2022). The stratum error rate will be described by arm.

Primary Analysis (Time to EDA)

Time to EDA is the duration between the date of the first administration of the experimental treatment and the date of EDA.

Date of EDA is:

- The date of the "conversion MRI" for patients with EDA determined by the appearance of NEL on MRI without having a relapse during the follow-up,

- The date of the first symptoms of a relapse for patients with EDA determined by a new relapse without the appearance of NEL on MRI during the follow-up,

- The earlier of the two dates between the date of the first symptoms and the date of the MRI showing NEL for patients who have both a relapse and NEL on MRI during the follow-up.

Patients lost to follow-up or not showing EDA during the follow-up will be right-censored at the date of the last news. The endpoint date will be established for each patient at the date of the end-of-study visit conducted 24 months (2 years) after inclusion.

Time to EDA in both arms will be graphically represented using the Kaplan-Meier method.

The proportional risk of EDA in the experimental arm compared to the placebo arm will be estimated along with its 95% confidence interval using a random-effects Cox model (random center effect) after checking the proportional hazards assumption. Adjustment will be made for the same variables as those used when analyzing the rate of EDA.

Secondary Analyses

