Secondary Objective A: Evaluate clinical efficacy on the number of relapses during the study period. The determination of the number of relapses is based on data from the EDA visit and the summary table of relapses based on the evaluation at Month 24. The number of relapses will be compared between the two arms using a non-parametric Mann-Whitney Wilcoxon test.

Secondary Objective B1: Describe the parameters of magnetic resonance imaging (brain and spinal cord MRI) at the "conversion MRI":

- Appearance of NEL on brain MRI in T2/FLAIR (including size increase) and/or on spinal cord MRI in T2 ("conversion MRI" Yes/No)

- New brain or spinal cord gadolinium-enhancing T1 lesions (active lesion(s) Yes/No)

- Lesion load in mm³ of each brain MRI from the FLAIR sequence

- Total number of gadolinium-enhancing T1 lesions (categorical measure: none, one, at least two)

Secondary Objective B2: Describe the magnetic resonance imaging (brain and spinal cord MRI) parameters during follow-up:

Normalized brain volume obtained from the 3D T1 sequence at different visits
Change in global brain volume (mm3, from the 3D T1 sequence) between the baseline examination and the 2-year examination on one hand, and between the 3-month examination and the 2-year examination on the other hand, to limit the effect of pseudo-atrophy after the first relapse

Secondary Objective C: Evaluate efficacy on disability progression, measured by the EDSS score and Kurtzke functional scores (Kurtzke 1983; Noseworthy et al. 1990; Goodkin et al. 1992) at baseline and during follow-up, then considering scores at M0 and M24 only.

Secondary Objective D: Evaluate efficacy on cognitive abilities (PASAT) (Cutter et al. 1999; Fischer et al. 1999; Parmenter et al. 2006) at baseline and during follow-up, then considering scores at M0 and M24 only.

Secondary Objective E: Evaluate efficacy on quality of life (EQ5D, SF36, TLS-QoL10, and TLS-COPING10 questionnaires), fatigue (FSMC questionnaire), and anxiety/depression (HADS questionnaire) at baseline and during follow-up, then considering scores at M0 and M24 only.

For Objectives C, D, and E:

- A first mixed-effects regression model will be used to compare the evolution of the outcome measures (EDSS score for Objective C, PASAT score for Objective D, and quality of life scores for Objective E). The model variables will include:
 - Scores at different visits (outcome variables)

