 - Treatment arm (explanatory variable of interest)
 - Center as a random effect (multiple patients per center)
 - Patient as a random effect (multiple measurements per patient)
 - Visit (temporal chronological variable)
 - Interaction between the treatment arm and the presence of a relapse during follow-

up

- A second mixed-effects regression model will be used to compare the M24 scores of the outcome measures while adjusting for baseline scores (M0):
 - M24 score (outcome variables)
 - Treatment arm (explanatory variable of interest)
 - Center as a random effect (multiple patients per center)
 - M0 score (adjustment variable)

- Interaction between the treatment arm and the presence of a relapse during follow-up

Secondary Objective F: Evaluate treatment tolerance on:

a. The occurrence of AEs and SAEs

- b. Pharmacological measurement of serum concentrations of 25(OH)D2 and 25(OH)D3
- c. Measurement of serum calcium, urinary calcium, and renal function

The number of AEs and SAEs per patient will be described by arm.

For points b and c, a mixed-effects regression model will be used to compare the evolution of measurements during follow-up. The model variables will include:

- Measurements at different visits (outcome variable)
- Treatment arm (explanatory variable of interest)
- Center as a random effect (multiple patients per center)
- Patient as a random effect (multiple measurements per patient)
- Visit (temporal chronological variable)

Secondary Objective G: Initial formulation: Correlate the variation in clinical and imaging parameters with the initial level and changes in the levels of 25(OH)D2 and 25(OH)D3 under treatment.

Reformulated Objective G1: Study the link between the severity of impairment (parameters measured by the baseline MRI, such as the number of lesions, EDSS score) and the vitamin D level measured during pre-screening (25(OH)D2 and 25(OH)D3).

A mixed-effects regression model will be estimated. The model variables will include: - Severity of impairment at inclusion (outcome variable). Several variables will be successively modeled: binary variables for MRI parameters (using a logistic regression model) and a quantitative variable for the EDSS score.

- Levels of 25(OH)D2 and 25(OH)D3 at pre-inclusion (explanatory variables of interest)
- Treatment arm (adjustment variable)
- Center as a random effect (multiple patients per center)

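### Secondary Objective A tests raw relapse counts with a Wilcoxon test that ignores time at risk and yields no effect estimate; a rate model would be a cheap improvement

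*SAP*

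**What the plan says.** Under Secondary Objective A the endpoint is the number of relapses over the study. The count "is based on data from the EDA visit and the summary table of relapses based on the evaluation at Month 24". The analysis is one sentence: "The number of relapses will be compared between the two arms using a non-parametric Mann-Whitney Wilcoxon test". No follow-up time, centre term, effect measure or confidence interval is named.

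Other parts of the SAP bear on this:

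- **Primary Analysis (Rate of EDA)** foresees patients who stop follow-up before two years and plans a sensitivity analysis for them.
- **Primary Analysis (Time to EDA)** deals with unequal follow-up by censoring: "Patients lost to follow-up or not showing EDA during the follow-up will be right-censored at the date of the last news". It also asks for a 95% confidence interval for the treatment effect.
- **Centre** is a stratification factor. It is a random effect in both primary models and in the between-arm models for Objectives C to F ("Center as a random effect (multiple patients per center").
- **The opening section** on description by arm prescribes "median and interquartile range for other quantitative variables" when a variable is not Gaussian.
- **Method for Handling Missing, Unused, or Invalid Data** limits its loss-to-follow-up rule to the primary outcome and plans no imputation for secondary outcomes.
- **Analysis population** includes everyone who took at least one dose.

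**The concern.** A raw count treats a patient seen for six months and one seen for two years as equally informative. If one arm is followed for less time, it shows fewer relapses for that reason alone, and a rank test on counts cannot separate this from a treatment effect. The SAP protects its time-to-event analysis against unequal follow-up but not this one.

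A Wilcoxon p-value also does not say by how much the relapse rate changed. For a clinical efficacy endpoint that is the number readers want. Finally, the SAP does not say in so many words how a treated patient without a Month 24 evaluation enters the count. At stake are the power, the interpretability and, under clearly unequal loss, the error rate of a secondary result.

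**Working it through.** The SAP gives no relapse rate, dropout share or power for this objective, so there is no figure to reproduce. Everything below except the 316 patients and the 0.05 level is an assumption.

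**Inputs.** 316 patients (Primary Analysis, Rate of EDA, lesion-load paragraph); equal allocation assumed, 316/2 = 158 per arm; two-sided 0.05; two years of follow-up; gamma-Poisson counts with dispersion 1 unless stated; dropout independent of relapse. Loss is written active/placebo.

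**1. What unequal loss does to raw counts when treatment has no effect.** Let dropout times be uniform from 0.05 to 2 years, mean (0.05 + 2)/2 = 1.025. Mean follow-up with loss share d is 2(1 − d) + 1.025d.

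- 10/20: 1.9025 and 1.805 years; placebo/active count ratio 0.949.
- 10/30: 1.9025 and 1.7075; ratio 0.898.
- 5/35: 1.951 and 1.659; ratio 0.850.

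The arm that loses more patients shows 5% to 15% fewer relapses with no true difference.

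**2. Type I error** (placebo rate 0.2, then 0.4 relapses/year; 2,000 runs for the Wilcoxon test, 500 for a negative binomial model with log-time offset and dispersion set at its true value):

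| Loss | Wilcoxon, observed counts | Wilcoxon, completers only | Rate model |
|---|---|---|---|
| 0/0 | 4.3%, 5.3% | 5.1%, 4.8% | 3.8%, 4.0% |
| 15/15 | 5.4%, 5.7% | 5.0%, 5.0% | 6.4%, 5.6% |
| 10/20 | 5.2%, 6.5% | 4.3%, 4.5% | 4.8%, 6.2% |
| 10/30 | 8.8%, 9.7% | 5.7%, 4.9% | 4.6%, 6.2% |
| 5/35 | 11.9%, 16.4% | 5.0%, 4.8% | 4.6%, 4.8% |

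A separate simulation gave 5.1% at 15/15, 6.4% at 10/20 and 15.4% at 5/35 for the Wilcoxon test on observed counts.

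**3. Power under equal loss** (0.2 vs 0.3 relapses/year, exponential dropout, 30 centres, both tests set to a true 5% size), Wilcoxon vs negative binomial with offset and random centre:

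- No loss: 46% vs 54% without a centre effect; 42.5% vs 50.4% with centre log-rate SD 0.5.
- 15/15: 42% vs 48%, and 37% vs 46%.

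Over placebo rates of 0.15 to 0.5 per year and dispersion 0.5 to 2 (15/15 loss, centre SD 0.3), the gap runs from 2.5 to 10.5 points at true size and from 4 to 14 at nominal size. The centre term supplies 1 to 2 of these points at SD 0.5 and none at SD 0.

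**4. Power under unequal loss** (same rates, nominal 5%, no centre effect):

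| Loss | Wilcoxon, observed counts | Wilcoxon, completers only | Rate model |
|---|---|---|---|
| 10/20 | 32% | 41% | 53% |
| 20/10 | 54% | 40% | 50% |

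Only the observed-count test moves. Its gain at 20/10 is not efficiency: the active arm has less time in which to relapse.

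**5. Can the description by arm fill the gap?** With dispersion k and mean m over two years, P(0) = (1 + km)^(−1/k). At 0.3 and 0.2 per year with k = 1, P(0) = 1/1.6 = 62.5% and 1/1.4 = 71.4%, so both arms have median 0 and interquartile range 0 to 1. At 0.5 per year with k = 0.5, P(0) = 1.5^(−2) = 44%, so the placebo median is 1; at two-thirds of that rate P(0) = 56%, median 0. The summary is uninformative at low rates but not always. In no case is it a between-arm estimate.

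**6. The counting rule.** The population rule covers all treated patients and is not confined to the primary outcome. Its exclusion list concerns patients without follow-up, and lacking a Month 24 evaluation is not on it. No imputation is planned. The EDA visit is a second source of relapses. Read together, these favour counting what was observed. What they do not state is how a treated patient without a Month 24 evaluation enters the count: one who left early with no EDA visit, or one whose relapses after the EDA visit were never tabulated.

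**The case against.** The best defence is that a Wilcoxon test for a secondary count is a legitimate analyst's choice. Under equal, non-informative loss it holds its level, and the SAP gives no reason to expect unequal loss. That stands, and it limits the point to power, interpretability and robustness.

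The power comparison also favours the proposed model. The data were generated in essentially the form the model fits, and neither relapse-dependent dropout nor a relapse rate that changes after EDA was tried. This stands too: the 3 to 10 points are partly a best case.

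A reader might infer that the counting rule is wholly open, so that an analyst could choose the favourable version afterwards. The population and no-imputation rules do not support that; the gap is narrow, and the protocol, not shown here, may close it. A reader might also infer that counting and excluding respond in opposite ways to unequal loss. They do not: excluding stays near 40%, and only counting moves.

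The missing centre term is a real inconsistency with the other models, but its effect is small.

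None of this answers two gaps: time at risk is ignored in a trial whose plan foresees early discontinuation, and no effect size is planned.

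**Conclusion.** The point holds as a cheap improvement to a secondary analysis. The primary result is unaffected.

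- **Equal, non-informative loss:** the level is kept, with roughly 3 to 10 points of power lost at assumed rates.
- **Unequal loss:** power depends on which arm loses more, and type I error is about 6% at 10/20 and about 15% at 5/35. The rate model changes little.
- **Any loss pattern:** no rate ratio or confidence interval will be available from the plan as written.

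It would go too far to call the Wilcoxon test invalid here. That would need clearly unequal loss, and the SAP gives no dropout figure. It would equally go too far to say that its level is safe, since that holds only for equal or mildly unequal loss.

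**What to change.** Replace the analysis sentence under Secondary Objective A with wording such as:

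> Relapse counts will be compared by negative binomial regression (Poisson with robust variance if it does not converge) on treatment arm, with centre as a random effect and, as offset, the log of time from first dose to the end of relapse ascertainment (Month 24 evaluation or, if absent, the last visit at which relapses were assessed). The rate ratio and its 95% CI will be reported. Patients without a Month 24 evaluation contribute their observed relapses over their observed time. Treated patients with no relapse assessment after first dose have no time at risk and are reported by arm. The Wilcoxon test on observed counts is a sensitivity analysis.

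The centre term is there for consistency with the other models; little gain is expected from it. If the Wilcoxon test stays as the main test, the minimum is to state the counting rule and add a rate ratio with 95% CI.

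**Cost.** SAP wording and one derived variable. The time-to-EDA variable cannot serve as the offset, because it ends at EDA: "Time to EDA is the duration between the date of the first administration of the experimental treatment and the date of EDA". The SAP shows a last-news date for patients without EDA, but no last relapse-assessment date for patients who had EDA and then left before Month 24, so its availability must be checked. The model adds a distributional assumption and does not correct for dropout related to relapse.
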